10.3. Statistical Analyses

A separate SAP will be developed, which will include a more technical and detailed description of the statistical analyses described in this section.

The primary efficacy endpoint of the trial is the proportion of patients by genotype who demonstrate a significant clinically meaningful response (defined below) to setmelanotide at the end of Stage 1:

- For all patients: $\geq 5\%$ reduction in BMI from Baseline

The 95% exact confidence interval will be provided for the primary efficacy endpoint. The analyses of the efficacy endpoints in Stage 1 will be performed based on the safety analysis set, and the analyses of the efficacy endpoints in Stage 2 will be performed based on the FAS, which is defined as all patients randomized in Stage 2 who received at least 1 dose of trial medication (placebo or setmelanotide) in Stage 2 and have baseline data.

AEs/SAEs will be summarized with frequencies and percentages. A by-patient AE data listing including onset and resolution dates, verbatim term, preferred term, treatment, severity, relationship to treatment, action taken, and outcome will be provided.

Safety data including laboratory evaluations and vital signs assessments will be summarized by time of collection. In addition, change from baseline to any post-dose values will be summarized for vital signs and clinical laboratory results. Frequency of patients with abnormal safety laboratory results will be tabulated.

All safety analyses and summary tables will be based on the safety analysis set.

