All patients who are screened (including screen failed).

- **Safety Analysis Set**

All patients who received at least one dose of trial medication.

- **Safety Analysis Set Enrolled in Stage 2**

All patients from Safety Analysis Set who enrolled in stage 2 and received at least one dose of trial medication in stage 2.

- **Full Analysis Set (FAS)**

All patients randomized in Stage 2 who received at least one dose of trial medication (placebo or setmelanotide) after randomization in Stage 2 and have baseline weight data. Analyses performed on the FAS will be based on patients as randomized.

- **Supplemental Analysis Set (SAS)**

All patients who are eligible after the re-confirmatory genetic diagnosis.

M. Special Distribution Schedule

Hunger Questions and [REDACTED] will be recorded as:

Stage 1

Daily [Scenario 1] during the Screening Period, [Scenario 2] for 7 consecutive dates after the enrollment visit, [Scenario 3] for 7 consecutive days starting at Study Days 28, 56, and 84, and [Scenario 4] up to 14 consecutive days starting at Study Day 98. These questionnaires should be completed prior to the morning meal (after an 8-hour fast) and prior to dosing in the morning. During the Screening Period, the patient must complete these questionnaires at least 4 of the 7 days prior to V1 (enrollment visit). If a patient completes V7 (Week 16), and is not continuing into Stage 2 of the trial, the patient will stop completing these questionnaires after completing V7 (and return the electronic diary, if applicable).

Stage 2

[Scenario 2] for 7 consecutive days starting at Study Days 140, 168, 196, 224, and 252, and [Scenario 4] up to 14 consecutive days starting at Study Day 266 (Week 38). These

questionnaires should be completed prior to the morning meal (after an 8-hour fast) and prior to dosing in the morning. All patients will stop completing these questionnaires after Visit 14 (Study Day 280), regardless of whether they have completed the full 14 days of data entry (and return the e-diary, if applicable) or at their Early Termination Visit (if applicable).

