The summary statistics displayed will be a function of the type of data associated with the summarized assessment. Unless stated otherwise in relevant sections to follow, continuous data will be summarized with the number of nonmissing values, mean, standard deviation, minimum, first quartile (Q1), median, and maximum, third quartile (Q3). Categorical data will

be summarized with the number of nonmissing values and the numbers of values equal to each of the possible values. Percentages of patients with each of the possible values will be calculated from the number of patients in the corresponding analysis population, unless stated otherwise. Some continuous variables may also be grouped into categorical levels and evaluated in frequency tables.

O. Blinded Review of Data

After all study data have been collected but prior to examining any study outcome data by treatment group, the data will be reviewed by the study statistician to determine whether any clarifications or changes to the analysis plan are needed. Any revisions made to the analysis plan as a result of the blinded review of the data will be documented.

P. Software Version

All analyses will be conducted using SAS Enterprise Guide 7.1 (64-bit) or SAS version 9.4 (64-bit).

Q. Gene Cohort Analysis

Gene cohort in this SAP is defined as group of patients with specified primary gene(s). In details, please see below for the grouping:

Gene Cohort	Genotype
SEMA3 Pathway	NRP1, NRP2, PLXNA1, PLXNA2, PLXNA3, PLXNA4, SEMA3A, SEMA3B, SEMA3C, SEMA3D, SEMA3E, SEMA3F, SEMA3G
PHIP	PHIP
SIM1	SIM1
MAGEL2	MAGEL2
Other	TRPC5, MRAP2, HTR2C, KSR2, TBX3, LEP, ISL1, DNMT3A, MECP2, MC3R, CPE, RPGRIP1L, CREBBP, TUB

After a patient enrolls in the trial, the pre-identified primary gene is reconfirmed or may be reclassified with the [REDACTED] and manual blind review during the trial. A supplemental analysis with the re-confirmative classification of genes will be conducted.

VI. Patient Accountability

All patients in safety analysis set will be used for below analyses unless otherwise specified. The table and listing display for all analyses below will follow section V.N unless otherwise specified.

A. Patient Demographic and Baseline Characteristics

Patient demographic and baseline characteristics will include the patient's age [6 to <12, 12 to <18, and 18 to ≤65 years of age], sex [Child-bearing potential if female], ethnicity, race, weight

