[REDACTED]

[REDACTED]
[REDACTED]

[REDACTED]

within same PT. AE missing relationship will be imputed as 'Related'. AE missing CTCAE grade will be imputed as 'Grade 3 - Severe'.

An overall summary will be prepared for the following type of AEs :

- Any TEAE
- Any TEAE related to study drug
- Any serious TEAE
- Any serious TEAE related to study drug
- Any TEAE with CTCAE grade 3 or higher
- Any TEAE leading to drug permanently discontinued
- Any TEAE leading to drug permanently discontinued and related to study drug

Separate summaries will be prepared for the following types of treatment-emergent AEs by stage and treatment group:

- By SOC and PT
- By SOC and PT for study drug related events
- By SOC and PT for serious events
 - By SOC and PT for treatment related serious events
- By SOC, PT and maximum CTCAE grade
 - By SOC, PT and maximum CTCAE grade for study drug related events
- By SOC and PT for event with CTCAE grade 3 or higher
- By SOC and PT for events leading to drug permanently discontinued
 - By SOC and PT for study drug related events leading to drug permanently discontinued

All AE data will be listed in one listing by cohort and treatment and a column to indicate the period of the AE occurs. Separate AE listings will be created for SAE, AE with CTCAE Grade 3 or higher and AE leading to Drug Permanently Discontinued.

C. Injection Site Evaluation

Frequency and percentage of injection site reaction (including Erythema, Edema, Induration, Itching, Pain or Tenderness, Other) will be tabulated by no reaction or severity (mild, moderate, and severe) by stage and visit. Percentage is based on the number of patients with assessment performed within each visit.

Injection site reaction data will be presented in listing by stage.

D. Clinical Laboratory Results

Laboratory test results include hematology, coagulation, clinical chemistry, and urinalysis.

Blood samples for a fasting glucose, [REDACTED] measurements will be obtained at the time points designated in the [REDACTED]

SOA. They will follow the analysis in section VII.D and will be analyzed separately from laboratory data.

Antidrug antibody will be summarized by visit and be listed separately from laboratory data.

Summaries of actual values and changes from baseline within stage will be presented by stage and visit according to SOA. Similarly, summary statistics for the eGFR will be provided.

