- Any medications happening after the dosing date at visit 14 will not be considered as concomitant medication in stage 2

Concomitant medications will be tabulated by ATC Level 2 classification and PT by stage. A patient having more than one medication within the same ATC Level 2 or preferred term will be counted only once for that ATC Level 2 or preferred term.

A listing of prior and concomitant medications will be provided.

H. Concomitant Procedures

Concomitant procedures data will be listed by stage. The definition of stage will follow adverse events in IX.B.

I. Skin Examination

A comprehensive skin examination will be performed by the Investigator at the time points designated in the SOA.

The skin examination should include a full body (head-to-toe skin examination).

Frequency count of most severe outcome across all skin regions within patients will - be provided by stage and visit. The severity of the outcome is rated as Abnormal, CS > Anormal, Not CS > Normal > Not Done.

Also, the frequency count by skin region with abnormal result will be provided.

All skin examination data will be presented in listing.

J. Hyperpigmentation

Hyperpigmentation form will be administered at postbaseline visits.

All hyperpigmentation data will be presented in listing.

K. Sexual Function

Sexual function forms have different versions between male and female. All sexual function data will be presented in listing by version.

L. Electrocardiogram

A single 12-lead electrocardiogram (ECG) is performed at the visits designated in the SOA.

ECG measurements include PR interval (msec), RR interval (msec), QRS interval (msec), QT uncorrected (msec), QT corrected with Bazett's formula (msec), QT corrected with Fridericia formula (msec). Summaries of actual values and changes from baseline of these measurements will be presented.

A frequency and percentage table of normal, abnormal not clinically significant and abnormal clinically significant for overall ECG evaluation will be tabulated.

ECG data will be presented in listing.

M. Columbia-Suicide Severity Rating Scale (C-SSRS)

The C-SSRS that will be administered to patients ≥ 6 years of age according to the SOA.

There are two versions of the C-SSRS forms:

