1. The Baseline/Screening version of the scale is the initial form of the instrument to assess suicidality in a patient's lifetime. This version can assess a patient's lifetime suicidality for data collection purposes as well as eligibility based on inclusion/exclusion criteria.
2. The 'Since Last Visit' version of the scale assesses suicidality since the patient's last visit. This version is meant to assess patients who have completed at least 1 initial C-SSRS assessment and should be used in subsequent visits. The 'Since Last Visit' version of the C-SSRS is inquiries about any suicidal thoughts or behaviors the patient/participant may have had since the last time the C-SSRS was administered.

A frequency and percentage table and a shift from baseline by visit will be provided to display the number of patients who have answered at least one 'Yes' to: Suicidal Ideation (1-5),

Suicidal behavior (6-10), either have suicidal ideation or suicidal behavior (1-10), and the question “Non-Suicidal Self-Injurious Behavior”.

In details, the Suicidal Ideation and Suicidal behavior will include questions as below:

Suicidal Ideation (1-5)

1. Wish to be dead
2. Non-Specific thoughts
3. Ideation without intent to act
4. Ideation with some intent to act
5. Ideation with specific plan

Suicidal behavior (6-10)

6. Preparatory acts or behavior
7. Aborted attempt
8. Interrupted attempt
9. Actual attempt
10. Completed suicide

All C-SSRS data will be listed.

N. Patient Health Questionnaire-9 (PHQ-9)

The PHQ-9 is a 9-item depression scale of the Patient Health Questionnaire and will be used for patients ≥ 12 years of age. After the patient has completed the PHQ-9 questionnaire, it is scored by the trial staff. Any patient with a PHQ-9 score ≥ 10 will be referred to a mental health professional (MHP). The PHQ-9 will be administered according to the SOA.

Summary statistics for the score of summation of the 9 items and changes from baseline will be provided. Frequency count and percentage of number of patients with score ≥ 10 will also be included. Only scores with all 9 items answered will be summarized.

All PHQ-9 data will be listed.

O. Children’s Depression Inventory-2 (CDI-2)

The CDI-2 has both a self-report and a parent version.

The CDI-2: Self-Report Short version is an efficient screening measure that contains 12 items and will be administered to patients < 12 years of age according to the SoA.

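### ECG, C-SSRS and PHQ-9 percentages default to all dosed patients as denominator, so they understate the rate among patients actually assessed

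*SAP*

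**What the plan says.** SAP V.N (Data Display Characteristics) says that categorical data will "be summarized with the number of nonmissing values and the numbers of values equal to each of the possible values". It then fixes the denominator: "Percentages of patients with each of the possible values will be calculated from the number of patients in the corresponding analysis population". The sentence closes with an escape clause, "in the corresponding analysis population, unless stated otherwise".

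The population for safety tables is set in Protocol Section 10.3: "All safety analyses and summary tables will be based on the safety analysis set". SAP V.L defines that set as "All patients who received at least one dose of trial medication". It also defines a version restricted to patients dosed in Stage 2. No set is restricted by age or by having been assessed.

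In the readable safety text, one table uses the escape clause. For injection-site reactions, IX.C says: "Percentage is based on the number of patients with assessment performed within each visit". Three other tables promise percentages without naming a denominator:

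- **ECG (IX.L):** "A frequency and percentage table of normal, abnormal not clinically significant and abnormal clinically significant for overall ECG evaluation will be tabulated".
- **C-SSRS (IX.M):** a frequency and percentage table by visit.
- **PHQ-9 (IX.N):** the number and percentage of patients scoring 10 or more. IX.N adds "Only scores with all 9 items answered will be summarized", and all PHQ-9 data are listed.

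The trial enrolls ages 6 to 65 (Protocol Section 6.1). The PHQ-9 is for patients aged 12 and older, and younger children take the CDI-2 (Protocol Sections 8.9.9.2 and 8.9.9.3).

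**The concern.** When the denominator is everyone dosed, a patient with no assessment counts in the percentage as a patient without the finding. The printed rate is then lower than the rate among those examined, and it falls further at later visits as patients leave. For the PHQ-9 there is a second dilution, because children who are never given the scale sit in the denominator.

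Three features of the plan make this more than a formality:

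- Protocol Section 8.9.9 expects that some patients cannot complete the C-SSRS or PHQ-9 and lets the investigator skip them.
- Patients whose BMI rises by at least 5% in Stage 2 are offered open-label treatment and may leave for the extension trial. SAP V.E maps early-termination records by actual study day, and the Week 40 window opens at Day 266. An earlier leaver is therefore absent from a Week 40 row but remains in its denominator.
- Stage 2 tables are split by treatment and gene cohort (V.N), so cells are small and a few losses move a percentage a long way.

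ECG, C-SSRS and PHQ-9 data also go unblinded to the DSMB (V.I). If those outputs follow V.N, patients who have not yet reached a visit would be in its denominator too.

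A PHQ-9 form with a blank item drops out of the numerator while its patient stays in the denominator. A patient whose answered items already total 10 or more is then counted, in effect, as below 10.

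**Working it through.** The documents contain no figure to reproduce: no dropout rate, age mix or expected abnormality rate. The check is arithmetic on the stated rule, with assumed inputs shown as ranges.

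**Formula.** Let p be the rate among patients assessed, c the share of the set aged under 12 (PHQ-9 only; zero for ECG and C-SSRS), and d the share of eligible patients not assessed.

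Printed % = p × (1 − c) × (1 − d)

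**PHQ-9, p = 10%:**

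| c (under 12) | d = 0% | d = 10% | d = 20% | d = 30% |
|---|---|---|---|---|
| 5% | 9.5% | 8.55% | 7.6% | 6.65% |
| 10% | 9.0% | 8.1% | 7.2% | 6.3% |
| 20% | 8.0% | 7.2% | 6.4% | 5.6% |
| 30% | 7.0% | 6.3% | 5.6% | 4.9% |

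For example, 10% × 0.70 × 0.70 = 4.9%.

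**ECG and C-SSRS, p = 10%, c = 0.** The table prints 9%, 8% or 7% when 10%, 20% or 30% are not assessed.

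**Stage 2, equal rate of 15% in both arms, 10% not assessed on setmelanotide:**

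| Placebo not assessed | Setmelanotide prints | Placebo prints |
|---|---|---|
| 10% | 13.5% | 13.5% |
| 20% | 13.5% | 12.0% |
| 30% | 13.5% | 10.5% |
| 40% | 13.5% | 9.0% |
| 50% | 13.5% | 7.5% |

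For example, 15% × 0.90 = 13.5% and 15% × 0.60 = 9.0%. The difference comes entirely from the denominator, and it vanishes when loss is equal.

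**In counts (assumed).** Take 200 dosed patients, 40 of them under 12, leaving 160 eligible, of whom 128 are assessed and 16 are at 10 or more.

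- Rate among assessed patients: 16/128 = 12.5%.
- V.N default: 16/200 = 8.0%.
- If 4 of those 16 forms are incomplete, the default prints 12/200 = 6.0%.
- The complete-form rate on the proposed denominator is 12/(128 − 4) = 12/124 = 9.7%, with the 4 reported separately.

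**The case against.** **Redaction.** Sections VI, VII and VIII each open by fixing the population and display rules. The matching opening of section IX is blacked out, so a section-wide denominator rule could be there. This limits certainty and is why the point is confined to the readable text. However, if a section-wide rule based on assessed patients existed, the IX.C sentence would be redundant.

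**Visible counts.** V.N promises the number of nonmissing values, so a careful reader could recompute the rate. That is true, but the printed percentage stays wrong.

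**PHQ-9 population.** A programmer might read the corresponding population as patients aged 12 or older. That is possible, but V.L defines no such set.

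**Consequence.** No statistical testing is planned. The primary and secondary endpoints, AE incidence and the PHQ-9 referral rule are untouched. V.O allows documented clarifications at blinded review. All of this stands and limits the weight of the point.

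**Neither denominator is neutral.** If leaving is related to weight regain, assessed patients are a selected group. This stands too, and is a reason to print the assessed n.

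Three stronger readings are tempting, and the documents do not support them:

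- *Every by-visit safety percentage is affected.* Injection-site tables already use assessed patients. The laboratory shift tables promise no percentages, and the skin tables promise counts only. Nor do IX.L and IX.N say that their percentages are by visit. If a single summary were meant, visit-level loss would matter less, although the age dilution would remain.
- *The placebo rate will shrink most.* The open-label offer applies regardless of assignment, and no attrition by arm is given. Greater placebo loss is plausible but assumed.
- *Incomplete PHQ-9 forms already at 10 should be added to the rate.* Adding only those forms, with no rule for incomplete forms below 10, would bias the rate upward. Restricting summaries to complete forms is a prespecified choice, and the forms remain in the listing.

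**Conclusion.** The point holds for three tables: ECG evaluation, C-SSRS, and PHQ-9 of 10 or more. Under V.N as written, their percentages count unassessed patients as free of the finding, and the PHQ-9 percentage also counts children who never take the scale.

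The actual size cannot be known from the documents. Over the assumed ranges (5% to 30% under 12, 0% to 30% not assessed), a 10% PHQ-9 rate prints between 9.5% and 4.9%. For ECG and C-SSRS the proportional understatement equals the share not assessed. A spurious difference between arms arises only if Stage 2 loss differs by arm. Moving from Stage 1 to Stage 2 does not itself shrink Stage 2 percentages if the Stage 2 safety set is used.

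The conclusion assumes that the redacted opening of section IX holds no overriding rule. It is a reporting defect in safety tables and bears on no efficacy conclusion, but it should be corrected before database lock.

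**What to change.** In IX.L, IX.M and IX.N, state that percentages are based on patients who had that assessment at that visit, as IX.C already does. For the PHQ-9, the base is patients aged 12 or older with a scored form at that visit. Print the assessed n beside each percentage. Keep the full set as denominator for the primary responder endpoint and for AE incidence.

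Leave the complete-form rule for the PHQ-9 rate as it is. Add a separate count of patients with an incomplete form whose answered items already total 10 or more. This count assumes that item scores cannot be negative, which the documents do not state, so the SAP should give the item scoring.

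The cost is a few SAP sentences and no new data. Some safety percentages will rise slightly, and they will describe assessed patients only, which is why the n must be shown with them.
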